8.3.11. Protocol-Specified Serious Adverse Events

All cases of Grade 3 or 4 mQTcF prolongation regardless of causality and treatment arm must be reported as an SAE for up to 28 calendar days after the last dose of study drug administered. All SAEs will be reported to Pfizer Safety by the investigator as described in previous sections, and will be handled as SAEs in the safety database.

8.4. Treatment of Overdose

For this study, an overdose is considered >120% of the scheduled dose of study treatment.

There is no specific treatment for an overdose. Management of glasdegib overdose should include symptomatic treatment and ECG monitoring.

In the event of an overdose, the investigator should:

1. Contact the medical monitor within 24 hours.
2. Closely monitor the participant for any AEs/SAEs and laboratory abnormalities for at least 5 half-lives or 28 calendar days after the overdose of study intervention (whichever is longer). Closely monitor the participant for any AEs/SAEs.
3. Document the quantity of the excess dose as well as the duration of the overdose in the CRF.
4. Overdose is reportable to Safety **only when associated with an SAE**.

Decisions regarding dose interruptions or modifications will be made by the investigator in consultation with the medical monitor based on the clinical evaluation of the participant.

8.5. Pharmacokinetics

No pharmacokinetic assessments will be conducted.

8.6. Pharmacodynamics

No pharmacodynamic assessments will be conducted.

8.7. Genetics

No genetic assessments will be conducted.

8.8. Biomarkers

No biomarker assessments will be conducted.

8.9. Immunogenicity Assessments

No immunogenicity assessments will be conducted.

8.10. Health Economics

No health economic assessments will be conducted

9. STATISTICAL CONSIDERATIONS

Detailed methodology for summary and statistical analyses of the data collected in this study is outlined below.

9.1. Statistical Hypotheses

Not applicable.

9.2. Sample Size Determination

Not applicable.

9.3. Analysis Sets

9.3.1. Safety Analysis Set

The safety analyses of participants from Study B1371019 and participants originating from Parent Study B1371012 will be conducted separately and independently of each other.

The safety analysis set will include all participants who receive at least one dose of study treatment after consenting to this Protocol Amendment 6.

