3. OBJECTIVES AND ENDPOINTS

Objectives	Endpoints
Primary:	Primary:
• To monitor the safety and tolerability of the investigational drugs in participants continuing study intervention from this study and participants originating from Study B1371012	• All AEs and SAEs

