6.6. Dose Modification

Every effort should be made to administer the study drug treatment according to the planned dose and schedule.

In the event of Grade 3 or Grade 4 non-hematologic, study-treatment-related toxicity, dosing may be delayed and/or dose reduced. The glasdegib dose should be reduced 1 dose level at a time, in increments of 25 mg (75 mg QD, 50 mg QD, in the form of 3 or 2 x 25 mg tablets respectively). Glasdegib does not need to be delayed or dose reduced for hematologic, study-treatment-related toxicity.

Glasdegib may be interrupted or permanently discontinued for any reason as per GCP. Glasdegib should be permanently discontinued if:

interruptions are for more than 28 consecutive days when not required by the protocol (ie, HSCT period).

Dose escalations will not be allowed following glasdegib/placebo dose reductions. Dose modifications may occur in 3 ways:

Within a cycle: Dosing interruption until adequate recovery followed by dose reduction (if required) of glasdegib during a given treatment cycle.

Between cycles: The next treatment cycle may be delayed if toxicity from the preceding cycle persists.

In the next cycle: Dose reduction may be required based on toxicities experienced in the previous cycle.

When chemotherapy is given, a Cycle is determined by chemotherapy administration schedule. A Cycle is 28 days, but will be extended if there are dose delays or modifications in the chemotherapy backbone.

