8.3.1. Time Period and Frequency for Collecting AE and SAE Information

The time period for actively eliciting and collecting AEs and SAEs (“active collection period”) for each participant begins from the time the participant provides informed consent, which is obtained before the participant’s participation in the study (ie, before undergoing any study-related procedure and/or receiving study intervention), through and including a minimum of 28 calendar days after the last administration of the study intervention.

Follow-up by the investigator continues throughout and after the active collection period and until the AE or SAE or its sequelae resolve or stabilize at a level acceptable to the investigator and Pfizer concurs with that assessment.

For participants who are screen failures, the active collection period ends when screen failure status is determined.

If the participant withdraws from the study and also withdraws consent for the collection of future information, the active collection period ends when consent is withdrawn.

If a participant definitively discontinues or temporarily discontinues study intervention because of an AE or SAE, the AE or SAE must be recorded on the CRF and the SAE reported using the CT SAE Report Form.

Investigators are not obligated to actively seek AEs or SAEs after the participant has concluded study participation. However, if the investigator learns of any SAE, including a death, at any time after a participant has completed the study, and he/she considers the event to be reasonably related to the study intervention, the investigator must promptly report the SAE to Pfizer using the CT SAE Report Form.

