9.4.1. Safety Endpoint(s)

All participants who receive any study treatment (safety analysis set) will be included in the summaries and listings of safety data. Overall safety profile and tolerability of azacitidine or glasdegib + azacitidine will be characterized by type, frequency, severity, seriousness, timing, and relationship to study therapy of AEs.

AEs will be classified using the MedDRA classification system. The severity of the toxicities will be graded according to the NCI CTCAE version 4.03.

In all summaries, emphasis will be placed on TEAEs (events occurring from Amendment 6 consent up to last dose + 28 days). AEs will be summarized by the frequency of participants experiencing TEAEs corresponding to body systems and MedDRA preferred term and by worst NCI CTCAE (version 4.03) grade.

AEs leading to permanent discontinuation of any study treatment, and SAEs will be considered with special attention. AE reporting, including SUSARs, will be carried out in accordance with applicable local regulations. Reasons for discontinuation from study treatment will be summarized by the frequency of participants with each reason described.

Descriptive statistics ie, number of non-missing values and number of missing values (ie, n [missing]), mean, median, SD, minimum, maximum and first and third quartile (Q1 and Q3) for treatment duration ([last dose date - first dose date after Amendment 6 consent +1]/7) will be provided.

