## 4. ANALYSIS SETS

The B1371019 and B1371012 participants will be analyzed separately and independently. Analysis sets and the applicable analysis using the analysis set is summarized in the table below.

Analysis Set	Population	Applicable Analysis (for additional information see Section 6 )
Safety Analysis (SA) Set	All participants who received at least one dose of study after consenting to participate in Protocol Amendment 6	Safety analysis for B1371019 Safety analysis for B1371012

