## **6. ANALYSES AND SUMMARIES**

Analyses for B1371019 and B1371012 will be conducted separately and independently.

All participants who receive any study treatment (safety analysis set) will be included in the summaries and listings of safety data. Overall safety profile and tolerability of azacitidine or glasdegib + azacitidine will be characterized by type, frequency, severity, seriousness, timing, and relationship to study therapy of AEs.

AEs will be classified using the MedDRA classification system. The severity of the toxicities will be graded according to the NCI CTCAE version 4.03.

In all summaries, emphasis will be placed on TEAEs (events occurring from Amendment 6 consent up to last dose + 28 days). AEs will be summarized by the frequency of participants experiencing TEAEs corresponding to body systems and MedDRA preferred term and by worst NCI CTCAE (version 4.03) grade.

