## **6.3. Safety Summaries and Analyses**

Unless otherwise specified, summaries of AEs and other safety parameters will be based on the safety analysis population by treatment arm.

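### The safety set requires a dose after Amendment 6 consent, so an already-treated participant with a fatal or treatment-ending event before redosing drops out of the AE summaries

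*Protocol*

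**What the plan says.** The only endpoint is "All AEs and SAEs" (Protocol 3), in participants who continue a treatment they already receive.

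- **Who is analysed.** Protocol 9.3.1: "The safety analysis set will include all participants who receive at least one dose of study treatment after consenting to this Protocol Amendment 6". SAP 4: "All participants who received at least one dose of study after consenting to participate in Protocol Amendment 6".
- **What uses that set.** SAP 6: "All participants who receive any study treatment (safety analysis set) will be included in the summaries and listings of safety data". SAP 6.3 adds that, unless otherwise specified, "summaries of AEs and other safety parameters will be based on the safety analysis population by treatment arm". The fatal-AE table in SAP 6.3.1.1 falls under that rule. SAP 6.2.2 and 6.2.2.1 place disposition and treatment discontinuation on the same set. SAP 6.3.2 plans no separate death summary.
- **When events start to count.** Under Protocol 8.3.1, AE collection "begins from the time the participant provides informed consent". Protocol 9.4.1 and SAP 6 describe TEAEs as "events occurring from Amendment 6 consent up to last dose + 28 days". SAP 3.3 and 3.3.1, to which SAP 6.3.1 refers for its definition, start the window at the first non-zero dose instead, and send events outside it to listings only.

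**The concern.** Requiring a dose is natural in a first-exposure trial, where nobody has been exposed before consent. Here everyone has been, so a participant can have a drug-related event after Amendment 6 consent without a post-consent dose. Whether that dose is given can depend on the event itself. If toxicity resolves, the participant is redosed and enters the set. If it is fatal or ends all treatment, the participant never enters.

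At stake is the count of the most serious outcomes in a very small descriptive safety report. An omitted case leaves both numerator and denominator, and the outcomes that cause the omission are the severe ones, so those counts can only be understated.

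**Working it through.** The plan has no sample size, rate or error level to reproduce (Protocol 9.1 and 9.2 set none). The check is first textual, then a scale calculation on stated assumptions.

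**1. Two participants under each TEAE window.** A has a mild event after consent and is then redosed. B has a fatal event after consent and is never redosed.

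| Reading of the window | A's event | B's event |
|---|---|---|
| Protocol 9.4.1 and SAP 6: from consent | summarised | not summarised; B is outside the set |
| SAP 3.3, first dose taken as first after consent | listed only | not summarised; B is outside the set |
| SAP 3.3, first dose taken as earliest ever (SAP 3.2 does not mention consent) | summarised | not summarised; B is outside the set |

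B is lost under all three readings. Different treatment of A and B arises under two of them.

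**2. Can there be a gap between consent and the next dose?**

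- Glasdegib is daily (Protocol 6.1.2), so the gap is about 1 day if it is not interrupted.
- Azacitidine is given on 7 of 28 days, which leaves 28 − 7 = 21 dose-free days. With the +14-day visit window in the Schedule of Activities, this is 21 + 14 = 35.
- Under Protocol 6.6, "The next treatment cycle may be delayed if toxicity from the preceding cycle persists". Section 6.6.1 allows glasdegib to be held for up to 28 consecutive days.
- The Schedule of Activities marks re-consent at Screening and Day 1 and states no interval between them. No eligibility criterion in 5.1 or 5.2 specifically excludes consent during a hold.
- Exclusion requires that no further dose of either drug is given. Someone who stops glasdegib but goes on to azacitidine (Protocol 6.1.3) stays in the set.

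**3. Effect of one lost case: k/n becomes (k−1)/(n−1).** The event counts k are illustrative.

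- B1371019, at most 34: 3/34 = 8.8% becomes 2/33 = 6.1%.
- One arm of 17 (assumed even split of 34): 3/17 = 17.6% becomes 2/16 = 12.5%.
- B1371012, at most 3: 1/3 = 33.3% becomes 0/2 = 0%.

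**4. How likely is a lost case?** The documents give neither event rates nor consent timing. Let r be an assumed risk per 28 days of death or of stopping all treatment, and g the gap in days. Then p = 1 − (1−r)^(g/28), and P(at least one of n) = 1 − (1−p)^n. Example with r = 5%, g = 21, n = 17: p = 1 − 0.95^0.75 = 0.0377, and P = 1 − 0.9623^17 = 48%.

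| Gap for all 17 in an arm | r = 2% | r = 5% | r = 10% |
|---|---|---|---|
| 0 days (Day 1, just before dosing) | 0% | 0% | 0% |
| 1 day (uninterrupted glasdegib) | 1% | 3% | 6% |
| 21 days (azacitidine alone, consent just after Day 7) | 23% | 48% | 74% |

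The last row is an upper-end case, because it puts every participant at the start of the rest period. For the 3 from B1371012, a combination study, the 1-day gap gives 0.2%, 0.5% and 1.1%. The table shows that the answer depends almost entirely on when people re-consent, which the plan does not fix.

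**The case against.** **The SAP's own TEAE definition may remove the asymmetry.** If first dose in SAP 3.3 means the first Amendment 6 dose, set entry and event window open together, and no pre-dose event, mild or fatal, is summarised. This stands against a stronger reading that a reader might infer: that the plan builds in immortal time by counting mild pre-dose events and dropping fatal ones. The documents support that only under the consent-based window, and they contain both windows. It does not restore the lost participant.

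**The set is conventional.** Someone never redosed arguably did not continue under Amendment 6. This is a fair defence of keeping the set as primary. It is not a reason to leave undosed consenters unreported when the protocol collects their events from consent and counts them as enrolled on consent.

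**The event is not lost to oversight.** It reaches the CRF, and an SAE also goes to the sponsor's safety group (Protocol 8.3.1.1 and 8.3.1.2). SAP 3.3.1 would list it, although Protocol 9.4.1 and SAP 6 tie listings to the safety set. If it falls within 28 days of the last pre-consent dose, an Amendment 5 or B1371012 analysis might include it. Those analysis plans are not supplied, so this cannot be settled. All of this stands: the issue concerns summaries, not surveillance.

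**The phrase any study treatment.** A reader might see a second, looser definition of the set in Protocol 9.4.1 and SAP 6. The parenthesis that follows ties the phrase to the defined safety set, so there is no real contradiction.

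**Nothing is tested.** There is no hypothesis or formal comparison between arms, and entrants must be showing clinical benefit. This lowers the priority of the point.

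**Conclusion.** The point holds in a limited form. Whichever TEAE window applies, a participant with a fatal or treatment-ending event after Amendment 6 consent and before any further dose of either drug is absent from the AE, fatal-AE and discontinuation summaries. No planned summary recovers the case. SAP 6.2.2.1 does promise a count of patients enrolled overall, but SAP 6.2.2 places it on the safety set, and it carries no reasons.

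The size cannot be derived from the documents. It is near zero with Day 1 re-consent just before dosing, and larger on azacitidine alone or during holds and delays. The percentages above rest on assumed risks, an assumed 17/17 split and assumed consent timing. They show range only and do not estimate bias. A reader might infer a known bias against one arm of B1371019. The schedules make an uneven loss possible, but without consent timing the documents do not establish it.

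What can be said firmly is that one case is 1/34 = 2.9% of the larger group and 1/3 = 33.3% of the smaller. This is a cheap improvement to reporting, not a threat to the study's validity.

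**What to change.** 1. In SAP 4 and 6.2.2.1, report the number who consented to Amendment 6 but received no post-consent dose, with reasons, by arm for B1371019 and overall for B1371012.
2. Add a supportive summary of TEAEs, SAEs, fatal AEs and AE discontinuations in all previously treated participants who consented. Count events from consent to the end of the active collection period in Protocol 8.3.1. Do not require a dose within 28 days before consent, because such a rule would miss people who consent during a long delay. Section 8.3.1 gives the end of collection as a minimum of 28 days after the last dose, so the SAP should state the end used when that dose precedes consent. Flag any event also reported under Amendment 5 or B1371012, so that nothing is counted twice unnoticed.
3. Keep treatment duration on participants dosed after consent.
4. Reconcile the TEAE start in SAP 3.3 and 3.3.1 (first dose) with Protocol 9.4.1 and SAP 6 (consent), and say whether listings include consenters who were not redosed.

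The cost is a few sentences in the SAP, a matching note in the protocol and one extra set of tables. No new visits or data are needed, since collection already starts at consent. The downside is that a few participants who stop for non-safety reasons add short time at risk to the supportive denominator.

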9.4. Statistical Analyses

This section is a summary of the planned statistical analyses of the safety endpoints.

9.4.1. Safety Endpoint(s)

All participants who receive any study treatment (safety analysis set) will be included in the summaries and listings of safety data. Overall safety profile and tolerability of azacitidine or glasdegib + azacitidine will be characterized by type, frequency, severity, seriousness, timing, and relationship to study therapy of AEs.

AEs will be classified using the MedDRA classification system. The severity of the toxicities will be graded according to the NCI CTCAE version 4.03.

In all summaries, emphasis will be placed on TEAEs (events occurring from Amendment 6 consent up to last dose + 28 days). AEs will be summarized by the frequency of participants experiencing TEAEs corresponding to body systems and MedDRA preferred term and by worst NCI CTCAE (version 4.03) grade.

AEs leading to permanent discontinuation of any study treatment, and SAEs will be considered with special attention. AE reporting, including SUSARs, will be carried out in accordance with applicable local regulations. Reasons for discontinuation from study treatment will be summarized by the frequency of participants with each reason described.

Descriptive statistics ie, number of non-missing values and number of missing values (ie, n [missing]), mean, median, SD, minimum, maximum and first and third quartile (Q1 and Q3) for treatment duration ([last dose date - first dose date after Amendment 6 consent +1]/7) will be provided.

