6.1.3. Treatment Duration

Treatment with the study treatment should be continued until objective disease progression or relapse, death, unacceptable toxicity, or participant refusal, whichever occurs first.

If glasdegib is permanently discontinued for reasons other than objective disease progression, participant refusal, or consent withdrawal, single agent treatment with azacitidine may be continued if, in the Investigator's judgment, a clinical benefit has been observed and following discussion between the investigator and sponsor.

In cases of unacceptable toxicity or pregnancy, the participant must be withdrawn from study treatment.

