#### **3.3. Safety Endpoints**

Safety endpoints will be summarized based on the on-treatment period unless otherwise specified.

On-treatment is defined as the time from the first non-zero dose of study treatment to the last non-zero dose + 28 days.

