### 5.2. General Methods

For study B1371019, demographic data will be summarized by treatment arm and for both treatment arms combined. Disposition, exposure, and safety data will be summarized by treatment arm only. For study B1371012, summary will be provided for all participants continuing to Protocol Amendment 6.

The safety analyses of participants from Study B1371019 and participants originating from Parent Study B1371012 will be conducted separately and independently of each other.

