### **5.2.9. Analyses for Categorical Data**

Qualitative variables will be summarized by frequency counts and percentages. Unless otherwise specified, the calculation of proportions will include the missing category. Therefore counts of missing observations will be included in the denominator and presented as a separate category.

In case the analysis refers only to certain visits, percentages will be based on the number of patients with an assessment at that visit, unless otherwise specified.

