### **6.3.1. Adverse Events**

All analyses will be based on treatment emergent events unless otherwise specified. Treatment emergent is defined in [Section 3.3.1](#).

Seriousness, toxicity grade, study drug action taken (interruption, reduction, and withdraw) are as reported by the investigator on the adverse event CRF.

Summaries by treatment arm, SOC and PT in decreasing frequency based on the frequencies observed in the glasdegib arm will be provided for:

- Treatment Emergent Events by Maximum Toxicity Grade (All Causality);
- Treatment Emergent Events by Maximum Toxicity Grade (Treatment Related); Serious Treatment Emergent Events by Maximum Toxicity Grade (All Causality);
- Serious Treatment Emergent Events by Maximum Toxicity Grade (Treatment Related).

An event will be considered treatment related if the investigator considered the event related to the study drug or this information is unknown.

- Treatment Emergent Adverse Events Leading to Dose Interruptions by Maximum Toxicity Grade (All Causality) separately for each study drug, for chemotherapy, and for any study treatment;
- Treatment Emergent Adverse Events Leading to Dose Reductions by Maximum Toxicity Grade (All Causality) separately for each study drug, for chemotherapy, and for any study treatment;
- Treatment Emergent Adverse Events Leading to Permanent Withdrawal by Maximum Toxicity Grade (All Causality) separately for each study drug, for chemotherapy, and for any study treatment;
- Serious Treatment Emergent Events (All Causality).

Each patient will be counted only once within each PT.

As described in [Section 5.3.2](#), in case a patient has events with missing and non-missing toxicity grades, the maximum of the non-missing grade will be displayed. Missing grade will only be displayed in the event that only one event has been reported for a patient and the grade is missing.

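### For B1371019, adverse events are tabulated by arm as crude percentages with no time-at-risk denominator, although treatment is open-ended; adding participant-years and a few exposure-adjusted rates is a cheap improvement.

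*Protocol*

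**What the plan says.** Protocol 3 has one objective, safety, and one endpoint: "All AEs and SAEs". Protocol 9.4.1 states that "AEs will be summarized by the frequency of participants experiencing TEAEs", by body system, preferred term and worst grade. SAP 5.2.9 fixes the measure: "Qualitative variables will be summarized by frequency counts and percentages".

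The split by arm comes from the SAP and concerns B1371019 only. SAP 5.2 says "Disposition, exposure, and safety data will be summarized by treatment arm only", and SAP 6.3.1 plans "Summaries by treatment arm, SOC and PT in decreasing frequency based on the frequencies observed in the glasdegib arm". The participants from B1371012, at most 3, are summarised as one group.

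On length of observation, Protocol 6.1.3 says "Treatment with the study treatment should be continued until objective disease progression or relapse, death, unacceptable toxicity, or participant refusal, whichever occurs first". SAP 3.3 sets the window: "On-treatment is defined as the time from the first non-zero dose of study treatment to the last non-zero dose + 28 days". Under SAP 3.2 the last dose is that of whichever study drug is given last. Protocol 6.1.2 schedules azacitidine nominally on Days 1-7 of 28, with alternate schedules allowed, and glasdegib every day. Protocol 6 names only these two drugs as study interventions, so no placebo aligns the last-dose dates.

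Treatment duration is summarised in weeks (Protocol 9.4.1; SAP 6.2.3.1 for glasdegib, 6.2.3.5 for azacitidine), by arm under SAP 5.2. SAP 5.2.10 marks time-to-event analysis as not applicable. Protocol 9.4.1 and SAP 6 both list timing among the features of AEs to be described, but SAP 6.3.1 contains no summary of it.

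**The concern.** The share of participants with at least one event rises with the time they are watched. When that time is not fixed, two regimens with the same event rate can show different percentages because one group was treated or observed for longer. Here stopping may itself follow from toxicity, so an arm that is tolerated less well may be observed for less time and look better.

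The AE tables are the main output of Amendment 6. Their layout invites a side-by-side reading: rows are ordered on the glasdegib arm, and the disclosure table in SAP 6.3.1.1 has a cut-off of more than 5% in either arm. At stake is whether a reader takes a difference in observation time for a difference in tolerability, or misses a real one.

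**Working it through.** The plan has no sample size, power or rate to reproduce: Protocol 9.1 and 9.2 are not applicable, and 34 and 3 are caps. The check has four steps.

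**1. Window length under the SAP rule.** Suppose treatment stops on day s of the last cycle and azacitidine is given on Days 1-7. Counted from Day 1 of that cycle, the window ends on day min(s, 7) + 28 with azacitidine alone and on day s + 28 with daily glasdegib. The gap is max(0, s − 7) days.

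| Stop day s | Azacitidine alone | With glasdegib | Gap (days) |
|---|---|---|---|
| 7 or earlier | s + 28 | s + 28 | 0 |
| 14 | 35 | 42 | 7 |
| 21 | 35 | 49 | 14 |
| 28 | 35 | 56 | 21 |

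If stopping is uniform over the 28 days (assumed), the mean gap is (1 + 2 + … + 21)/28 = 231/28 = 8.25 days. Alternate azacitidine schedules can shrink the gap. It vanishes for a glasdegib-arm participant who goes on to azacitidine alone. It can exceed 21 days if a cycle is extended while glasdegib continues.

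**2. Effect of the maximum gap alone.** For N completed cycles the windows are 28(N − 1) + 7 + 28 = 28N + 7 days and 28N + 28 days. Assume the same constant hazard in both arms, so that the crude percentage is 1 − (1 − r)^(T/28), where r is the first-event risk per 28 days. The documents give no r; 10% is used here.

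| N | Windows (days) | Ratio | Azacitidine alone | With glasdegib | Gap (points) |
|---|---|---|---|---|---|
| 1 | 35 and 56 | 1.60 | 12.3% | 19.0% | 6.7 |
| 3 | 91 and 112 | 1.23 | 29.0% | 34.4% | 5.4 |
| 6 | 175 and 196 | 1.12 | 48.2% | 52.2% | 3.9 |
| 12 | 343 and 364 | 1.06 | 72.5% | 74.6% | 2.1 |

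With r from 5% to 20% and N from 1 to 12, the difference runs from 1.0 to 11.7 points, always higher with glasdegib.

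**3. Effect of unequal duration, same hazard.** The cycle numbers are assumed; the last column is glasdegib arm minus azacitidine-alone arm, in points.

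| Cycles, azacitidine alone and with glasdegib | Percentages at r = 10% | Difference at r = 5%, 10%, 20% |
|---|---|---|
| 3 and 6 | 29.0% and 52.2% | +14.8, +23.2, +27.5 |
| 12 and 6 | 72.5% and 52.2% | −16.5, −20.3, −14.5 |

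These figures take one fixed duration per arm. Spread within an arm also matters. With a hazard of 0.05 per month and fixed exposures of 12 and 6 months, 1 − exp(−0.05T) gives 45.1% and 25.9%, a gap of 19.2 points. With exponentially distributed exposures of the same means, 0.05/(0.05 + 1/12) = 37.5% and 0.05/(0.05 + 1/6) = 23.1%, a gap of 14.4 points.

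**4. Does person-time remove it?** A simulation used r = 10% in both arms, stopping uniform within the cycle, a geometric number of cycles with mean 6, and 200,000 participants per arm. Crude percentages were 41.1% (azacitidine alone) and 43.2% (with glasdegib). Participants with the event divided by time to first event or end of window gave 1.37 and 1.38 per participant-year, against a true −ln(0.9)/28 × 365.25 = 1.37. Under a constant hazard the artefact disappears.

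**The case against.** The strongest reply is that exposure is already reported by arm. In the azacitidine-alone arm, azacitidine duration plus 28 days is the SAP 3.3 window; in the other arm, glasdegib duration plus 28 days is close to it whenever glasdegib stops last. A reader might infer from the AE tables that nothing in the plan allows exposure to be judged; the documents do not support that. The help is only partial, however. The summaries are per drug, leave out the 28-day tail and are not tied to the AE rows, and time to first event cannot be recovered from them.

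Second, no between-arm inference is planned: there is no hypothesis, test, interval or tiered AE analysis, and the percentage with an event up to 28 days after treatment is a legitimate descriptive quantity. This stands, and it limits the harm to misreading.

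Third, rates would not make the arms comparable. Participants are unblinded and enter only if the investigator sees continuing benefit, so they are selected after randomisation. This also stands.

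Fourth, the window effect is below the data's resolution. With an assumed 17/17 split of the 34, one participant is 1/17 = 5.9 points, more than the window artefact at 6 cycles (3.9) or 12 cycles (2.1) when r = 10%. Sampling error is larger still: 8/17 has an exact 95% interval of 23% to 72%. It would be tempting to say that the rule gives every glasdegib participant 21 extra days; that holds only for a completed last cycle on nominal Days 1-7.

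**Conclusion.** The point holds as a reporting weakness. For B1371019 the sole endpoint is shown by arm without time at risk, and no planned summary supplies it in full. Unequal treatment duration is the larger potential distortion. It can act in either direction, and a two-fold difference in cycles moves the percentages by about 15 to 27 points in the examples above. Those sizes rest on assumed hazards and durations and are not estimates for this trial. The window rule is a smaller, one-directional addition of 0 to 21 days in a 28-day cycle, proportionally minor after several cycles.

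A reader might go further and conclude that the planned tables are biased against glasdegib, or that the arms were given different windows by design. The documents support neither. One common rule applies to both arms, its effect depends on when treatment stops, and the direction of any duration imbalance is unknown. This is a worthwhile improvement, not a flaw that invalidates the analysis.

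**What to change.** 1. Reconcile the start of the TEAE window before any person-time is computed. Protocol 9.4.1 and SAP 6 start it at Amendment 6 consent; SAP 3.3 starts it at the first non-zero dose. If a dose date is chosen, say that it is the first dose after Amendment 6 consent, as the duration formula in Protocol 9.4.1 does and SAP 3.2 does not.
2. In SAP 6.2.3, report total participant-years at risk per arm over that window, including the 28-day tail.
3. In SAP 6.3.1, add for any TEAE and any serious TEAE the exposure-adjusted incidence rate: participants with the event divided by participant-years to first event or end of window. Extend it to the more frequent preferred terms if wanted.
4. Keep the crude percentages, and state in a footnote that the arms are selected after randomisation and the figures are descriptive.

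The dates needed are already collected, and no visit, dose or clinical rule changes. The price is some programming, imprecise rates with at most 34 participants, an assumption of a roughly constant hazard, and reliance on some onset dates imputed under SAP 5.3.1. Limiting the rates to the main rows keeps that price small.
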